5.4 Reporting Procedures

The Principal Investigator will report any unanticipated events to the IRB as well as the Data and Safety Monitoring Board (DSMB) assembled for this study. When notified of an unanticipated event, the DSMB will convene and make a decision as to whether the study should continue. The IRB will also be notified of the DSMB's decision. Please see detailed Data and Safety Monitoring Plan.

5.5 Safety Monitoring

This study will leverage the standing Roybal Data and Safety Monitoring Board (DSMB) established by NIH. Reports of our safety measures will be delivered to our Data and Safety Monitoring Board at 6 and 12 months.

6. INTERVENTION DISCONTINUATION

Following each DSMB report, the board will make recommendations to the IRB as to whether the study should continue or if changes to the protocol are necessary for continuation.

[figure not shown]
7. STATISTICAL CONSIDERATIONS

7.1 Sample Size and Randomization

Sample Size: We conduct power on the discrete outcome of the referral. The rate of referrals for mental health and pain treatment is low at Northwestern, but if combined with sleep and physical therapy will be at least 5%. There are 300 clinicians who treat patients at the Northwestern outpatient clinics. There are also 5,159 persons over 65 years of age on long-term opioid therapy within patient registries at Northwestern University's health system with at least one primary care encounter in the past 12 months. Assuming 150 clinicians per condition, each treating 17 patients (i.e., 2,500 patients per condition), $\alpha = 0.05$ for a two-sided

test, an intraclass correlation coefficient of 0.06, and an 80% chance of detecting an effect, requires a 3% difference between groups when the baseline referral rate is 5% and 4% difference between groups when the baseline referral rate is 10% (see **Figure 2**).

Figure 2

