Behavioral insights: We hypothesize that the aspects of the patient's health that are assessed and discussed at the visit affect the type of care received. Evidence for this comes from two sources in the field of psychology: 1) similarity research and 2) linguistic labels. Similarity is an organizing principle for statements and judgments about patients.^{23,24} "This patient is like ... [*some referent*]" is a type of task ubiquitous in medicine. For high scorers on the Current Opioid Misuse Measure, the measure promotes a response from the treating clinician that "this patient is behaving like a misuser of opioids". Whereas, broader assessments such as Pain Tracker may produce more varied similarity statements, such as "This patient is behaving like a person who has experienced psychological trauma". Further, linguistic labels may play a role in the stability of judgments about persons. Nouns such as "misuser" may have a stronger and more lasting effect on the person's identity than verbs (e.g., "misuses").^{25,26}

3. **STUDY DESIGN**

We will conduct a 9-month randomized trial where persons age 65 or older on long-term opioid therapy (N= 1451 persons within the Northwestern Medicine Chronic Opioid Use registry system with at least one primary care encounter in the past 12 months ending 8/08/2023) receiving care from 286 clinicians will receive either the 1) Current Opioid Misuse Measure alone (Standard clinical practice /Control) or 2) COMM + Pain Tracker (intervention). We will assess the primary outcome in the electronic health record: referral rate to non-opioid related care, which includes mental health, physical therapy and sleep medicine referrals. We will also

measure the rate of new starts on antidepressants. Secondary outcomes include: 1) clinician aggregate monthly milligram (mg) morphine equivalent (ME) and 2) benzodiazepine prescribing.

SELECTION AND ENROLLMENT OF PARTICIPANTS

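### The stated 80% power assumes about 5,000 patients; the trial as described has 1,451 patients of 286 clinicians, which gives about 55% power for the stated differences

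*Combined protocol and SAP*

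**What the plan says.** Section 7.1 (Sample Size and Randomization) starts from two counts: "There are 300 clinicians who treat patients at the Northwestern outpatient clinics" and "There are also 5,159 persons over 65 years of age on long-term opioid therapy". It then computes power as follows: "Assuming 150 clinicians per condition, each treating 17 patients (i.e., 2,500 patients per condition". With two-sided alpha 0.05, an ICC of 0.06 and 80% power, it concludes that the trial "requires a 3% difference between groups when the baseline referral rate is 5" percent, and a 4-point difference when the baseline is 10%.

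Section 3 (Study Design) gives other numbers. The trial has "N= 1451 persons within the Northwestern Medicine Chronic Opioid Use registry system", with a primary care encounter in the 12 months ending 8/08/2023, "receiving care from 286 clinicians". Section 4.2.2 repeats 286 clinicians and sets randomization at the physician level, half to each arm. The eligibility window in section 3.1 matches the dated window of the 1,451.

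On the baseline, section 7.1 says: "The rate of referrals for mental health and pain treatment is low at Northwestern". It expects at least 5% once sleep and physical therapy are added. Section 7.3.1 defines the primary outcome as mental health, physical therapy and sleep medicine referrals, and does not list pain treatment.

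**The concern.** The two sections describe similar people: older long-term opioid users in Northwestern registries with a primary care encounter in the past year. One counts 5,159 and the other 1,451. Nothing explains the drop, and the power calculation was not rerun for the smaller number. The mean panel falls from about 17 patients per clinician to about 5.

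The power statement tells the IRB, the DSMB and later readers what a null result means. If it is wrong, a null result may be taken as evidence against differences of 3 to 4 points that the trial had little better than an even chance of detecting. The baseline has a separate problem: the 5% is given for a composite with an extra component, so it may not be the control rate of the primary outcome.

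**Working it through.** **Inputs.** Section 7.1: 150 clinicians per arm, 17 patients each, ICC 0.06, two-sided alpha 0.05, 5% versus 8% and 10% versus 14%. Section 3: 1,451 patients, 286 clinicians. Section 4.2.2: half of the clinicians to each arm.

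**Formulas.** With m patients per clinician and n patients per arm:
- design effect `DE = 1 + (m − 1) × ICC`
- effective sample size per arm `n_eff = n / DE`
- `SE = sqrt{[p1(1 − p1) + p2(1 − p2)] / n_eff}`
- `power = Φ(|p2 − p1| / SE − 1.96)`

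**Step 1: reproduce the plan's figures.**
- n = 150 × 17 = 2,550 per arm (the plan rounds to 2,500).
- DE = 1 + 16 × 0.06 = 1.96, so n_eff = 2,550 / 1.96 = 1,301.
- Detectable differences at 80% power are 2.7 points (5% baseline) and 3.5 points (10% baseline), which agree with the stated 3 and 4 as whole points.
- Power at exactly 3 and 4 points is 87.5% and 88.2%.

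Section 7.1 is therefore correct for its own inputs. The fault lies in the inputs.

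**Step 2: use the numbers in section 3.**
- Clinicians per arm: 286 / 2 = 143. Patients per arm: 1,451 / 2 = 725.5. Mean panel: 1,451 / 286 = 5.07.
- Share of the assumed patients: 1,451 / 5,100 = 28%.
- DE = 1 + 4.07 × 0.06 = 1.244, so n_eff = 725.5 / 1.244 = 583.
- 5% versus 8%: SE = sqrt[(0.0475 + 0.0736) / 583] = 0.0144; z = 0.03 / 0.0144 = 2.08; power 54.8%.
- 10% versus 14%: SE = sqrt[(0.0900 + 0.1204) / 583] = 0.0190; z = 0.04 / 0.0190 = 2.11; power 55.8%.
- Detectable differences at 80% power: 4.2 and 5.5 points.

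A pooled-variance test gives 54.7% and 55.6%. A t test with clinician-based degrees of freedom gives 54.6% and 55.5%.

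**Step 3: which change matters.** With 300 clinicians and 1,451 patients, power is still 55–56%. With 286 clinicians and 5,159 patients, it is 87–88%. The loss comes from the patient count.

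**Step 4: sensitivity.** The documents give no panel-size distribution and only one ICC, so the other values below are assumptions. For unequal panels, `DE = 1 + [(1 + CV²) × m − 1] × ICC`.

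| Scenario (286 clinicians, 1,451 patients) | Power, 5% vs 8% | Power, 10% vs 14% |
|---|---|---|
| ICC 0.06, equal panels | 55% | 56% |
| ICC 0 | 64% | 65% |
| ICC 0.10 | 50% | 51% |
| ICC 0.06, panel CV 0.6 | 51% | 52% |
| ICC 0.06, panel CV 1.0 | 46% | 47% |

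Over CVs of 0.6 to 1.0, the detectable differences are 4.4–4.8 points (5% baseline) and 5.7–6.2 points (10% baseline).

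**The case against.** The strongest objection is that 55% depends on counting one binary outcome per patient. Section 4.1 lists referral rates among the visit-level assessments, section 3.2 excludes visits, and section 7.4 plans a zero-inflated Poisson model of referral counts. If 5% versus 8% were rates per visit, an assumed 2 visits per patient would give about 75% power and 3 visits about 84%, ignoring within-patient correlation, which would lower both. This stands as a reason to call 55% the power in section 7.1's framing and not the power of the planned model. It does not support the claim as written: section 7.1 counts patients and compares proportions, and the documents give neither visits per patient nor a model-based calculation.

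Second, the documents do not say which population governs. The figure of 1,451 appears once, and the wording of section 7.1 (patient registries in general) is broader than that of section 3 (the named Chronic Opioid Use registry). The 5,159 could be an early planning count or a different registry definition. Section 3 is the likelier current figure, because its dated window matches the eligibility criteria and its 286 clinicians are repeated in section 4.2.2. If 5,159 is right after all, section 3 must be corrected instead. The two cannot both stand.

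Third, the pain-treatment mismatch is not quantified and contributes nothing to the 55%. That is correct. It affects which baseline to use, not the sample-size gap.

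Finally, a confidence interval would show the trial's true precision whatever the protocol says about power. That limits the harm after the results are in, but it does not make the stated power correct.

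**Conclusion.** The stated power is wrong for the trial that section 3 describes. With 143 clinicians per arm and 5.07 patients each, power for the stated 3- and 4-point differences is about 55% and 56%, against the 80% claimed and the 87–88% that the assumed inputs would give. The detectable differences are about 4.2 and 5.5 points, not 3 and 4.

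This rests on one binary outcome per patient, equal panels, an ICC of 0.06 and all 1,451 patients contributing. Unequal panels lower power further, and so would the active-cancer exclusion in section 3.2 if the 1,451 was counted before it. In the patient-level framing, no ICC restores 80%, since even an ICC of zero gives only 64–65%. The baseline rate should also be re-established for the three-component outcome; the documents do not show how far it would move.

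**What to change.** - Reconcile 5,159 patients and 300 clinicians (section 7.1) with 1,451 and 286 (section 3), and state which applies and why the count changed.
- If section 3 governs, rerun section 7.1 with 143 clinicians per arm, the observed panel-size distribution (mean 5.07) and ICC 0.06. Replace the 3- and 4-point statement with the detectable differences obtained (about 4.2 and 5.5 points if panels were equal), or state power of about 55% for 3 and 4 points.
- Remove the 5,159, 300 and 17 figures as the basis for power. If they are kept for the record, label them as superseded planning assumptions.
- Take the baseline from the historical rate of mental health, physical therapy and sleep medicine referrals combined, without pain treatment.
- State the unit and denominator of the referral rate, so that the calculation matches the analysis in section 7.4.

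The cost is protocol wording and a short recalculation. The stated power becomes less favourable; no new patients are needed, and allocation does not change.

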7.2 Interim analyses and Stopping Rules

No interim analysis will be conducted on primary or secondary outcomes. The DSMB is granted full power to recommend discontinuation of the study to the consolidated IRB if safety concerns are found. The study team will send the board a biannual report providing data on our safety measures. Following each report, the board will make recommendations to the IRB as to whether the study should continue or if changes to the protocol are needed.

7.3 Outcomes

7.3.1 Primary outcome

The primary outcome is the referral rate to non-opioid related care. This includes: mental health, physical therapy and sleep medicine referrals. We will also measure the rate of new starts on antidepressants.

7.3.2 Secondary outcomes

Secondary outcomes include: 1) clinician aggregate monthly milligram (mg) morphine equivalent (ME) and 2) benzodiazepine prescribing. We will estimate the daily milligram morphine equivalent for each clinician by summing the total number of daily morphine equivalents written within a monthly observation period divided by the number of 30 days. For example, suppose a clinician has three qualifying visits over three days in one month and prescribed as follows: Patient #1 is prescribed 200mg ME/day x 30 days, Patient #2 has tapered from 200 mg ME/day to now 100mg ME/day x 30 days and Patient # 3 is on a tapering plan from 60 to 30 mg ME/day and receives 50 mg ME/day x 15 days. The clinician's outcome for that month then equals:

$$\begin{aligned} & [(200 \text{ mg/day} \times 30 \text{ days}) + 100 \text{ mg/day} \times 30 \text{ days}) + (50 \text{ mg/day} \times 15 \text{ days})] \times [1 \text{ Month}/30 \text{ days}] \\ & = (300 \text{ mg} \times 1 + 100 \text{ mg} \times 1 + 50 \text{ mg} \times (\frac{1}{2})) = 425 \text{ mg MED}/[\text{Month}]. \end{aligned}$$

Oral buprenorphine will be excluded from the calculations as it relates to opioid use disorder treatment. Morphine equivalent dose will be computed by standard means described elsewhere.²⁸ Benzodiazepines will be handled similarly to monthly milligram morphine equivalents but with valium morphine equivalents. Qualifying pain visits will be captured by including all ICD-10 pain diagnostic codes and excluding active cancer diagnoses.

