7.4 Data Analyses

For inferential analysis, our *primary hypothesis* is that the proportion of non-opioid referrals will be greater among physicians treating patients who receive PainTracker. We evaluate this with a zero-inflated Poisson model to estimate the number of referrals to non-opioid related care which is then divided by the average number of referrals for each group to estimate the proportion. Our *secondary hypothesis* is that milligram morphine equivalent dose will decrease for persons on high doses of opioid therapy receiving PainTracker. We assume a linear mixed-effects hierarchical knotted spline regression model which offers a flexible way to accommodate non-linear trends before and after the introduction of the intervention.²⁰ This model places a knot at the intervention start date allowing slopes before and during treatment to vary for intervention and control. For our two-group study evaluating this outcome, monthly mean milligram morphine daily dose prescribed for intervention and control, we will place a knot at t^* , the start of the intervention, and evaluate for each comparison between groups:

$$Y = \beta_1 + \beta_2 \text{Time} + \beta_3(\text{Time} - t^*)_+ + \beta_4 \text{Group} + \beta_5 \text{Time} \times \text{Group} + \beta_6(\text{Time} - t^*)_+ \times \text{Group} + \eta + \text{error} \quad [1]$$

where $(z)_+$ is a truncated line function that equals z when z is positive and is equal to zero otherwise, and η is the clinic random effect.

8. **DATA COLLECTION AND QUALITY ASSURANCE**

8.1 **Data Collection Forms**

Data will be collected from electronic medical and billing records and completion rates of PainTracker and COMM surveys.

8.2 **Data Management**

Each of the participating sites will create an extract from their Electronic Medical or Billing Records of the Data Elements. These records will be transferred to the coordinating center as a one time HIPAA compliant limited data set at the end of the study. The CC has created programs and quality control queries for transforming all of the data into a standard model (Observational Medical Outcomes Partnership Common Data Model, version 5.3.1).

The electronic data system, Epic, will have native data capture formats.

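### The worked MME example in 7.3.2 contradicts itself (325 against 425), and the clinician total it illustrates does not isolate the change in high-dose patients hypothesised in 7.4

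*Combined protocol and SAP*

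**What the plan says.** Section 7.3.2 of the combined protocol and SAP makes the clinician's aggregate monthly morphine equivalent the first secondary outcome. The rule is "summing the total number of daily morphine equivalents written within a monthly observation period divided by the number of 30 days", giving one value per clinician per month.

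The worked example has three patients:
- "Patient #1 is prescribed 200mg ME/day x 30 days"
- "Patient #2 has tapered from 200 mg ME/day to now 100mg ME/day x 30 days"
- a third patient, on a taper from 60 to 30 mg/day, who "receives 50 mg ME/day x 15 days"

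The first line of the equation uses these amounts. The second line enters 300 mg for the first patient and ends at 425 mg for the month.

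On which visits count, 7.3.2 says "Qualifying pain visits will be captured by including all ICD-10 pain diagnostic codes", with active cancer excluded. It gives no dose restriction. Benzodiazepines are to be handled in the same way but "with valium morphine equivalents".

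In 7.4 the secondary hypothesis is that "milligram morphine equivalent dose will decrease for persons on high doses of opioid therapy receiving PainTracker". The variable to be modelled is the "monthly mean milligram morphine daily dose prescribed for intervention and control". Equation [1] contains time, a knot at the start of the intervention, group, their interactions and a clinic random effect.

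**The concern.** There are two separate problems.

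The first is in the example, which is the only worked specification of this outcome. Its two lines disagree, so a programmer who uses it as a test case cannot tell which line to match.

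The second is that outcome and hypothesis concern different things. The hypothesis is about dose in a particular kind of patient. The outcome is the volume a clinician writes for everyone with a qualifying visit. The total could fall because fewer patients were seen while nobody's dose changed. It could also stay level while doses fell in the patients of interest. In either case the result would be hard to interpret as an answer to the hypothesis, which is the only secondary hypothesis that 7.4 states.

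**Working it through.** **1. The example.** Inputs are from the narrative and first equation line of 7.3.2, with the rule outcome = sum of (daily dose × days) / 30.

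- Patient 1: 200 × 30 = 6000 mg
- Patient 2: 100 × 30 = 3000 mg
- Patient 3: 50 × 15 = 750 mg
- Outcome: (6000 + 3000 + 750)/30 = 9750/30 = **325**

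Second line as printed: 300 × 1 + 100 × 1 + 50 × ½ = 300 + 100 + 25 = **425**. The line is consistent within itself, so this is not a damaged character in the total. The difference is 425 − 325 = 100, and 100/325 = 30.8%.

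**2. Could another convention give 425?** With the first-line inputs:

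| Convention | Result |
|---|---|
| No division by 30 | 9750 |
| 31-day month | 314.5 |
| 28-day month | 348.2 |
| Mean per patient | 108.3 |
| Mean weighted by days (9750/75) | 130 |
| Patient 3 supplied for 30 days | 350 |
| Patient 3 at 60 mg/day | 330 |

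None does. The figure 425 appears if Patient 1 is entered at 300, as the second line prints. It also appears if Patient 2 is kept at 200, which contradicts the 100 printed in both lines.

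**3. What the total measures.** For N patients with mean contribution m, the total is N × m; here 3 × 108.3 = 325. It responds to N as well as to m. Two invented changes to the example show this. They are arithmetic only.

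- Patient 1's contribution falls from 200 to 100, and four further visits each add 25 mg/day × 30 days: 100 + 100 + 25 + 4 × 25 = 325. The total is unchanged although the largest contribution has halved.
- No dose changes, but Patient 2's visit falls in the following month: 200 + 25 = 225. The total falls by 100/325 = 30.8%.

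**4. Hypothesis against model.** Section 7.4 sets no high-dose cut-off and no subgroup. Equation [1] has no term for dose stratum, patient-level dose, panel size or number of visits. Elsewhere, 2.2 mentions 120 mg/day as background, 5.3 uses > 49 for adverse events, and 5.1 refers to high-dose patients without a number. None is tied to this outcome, and the choice matters: of the example's three patients, one is above 120 and all three are above 49.

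**5. Total or mean.** Section 7.3.2 defines a total per clinician. Section 7.4 names a monthly mean by arm. If that is the arm average of clinician totals, it is still not a dose per patient and still has no high-dose restriction. If it is a mean over patients, it is a different variable from the one in 7.3.2.

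**The case against.** **The arithmetic slip is harmless.** The rule, narrative and first line agree, so a program that follows them returns 325, fails against 425 and exposes the discrepancy. No analysis or power figure uses 425, and the text cannot exclude that 300 was meant throughout. This largely stands. It makes the example a minor correction and argues for asking that the lines be reconciled. It does not remove the inconsistency.

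**A reader might infer that the outcome cannot test the hypothesis at all.** The documents do not support that. A total is weighted by dose: in the example, the one patient above 120 mg/day is a third of the patients but 200/325 = 62% of the total. A fall in high-dose patients would therefore move the outcome. What holds is that the outcome does not isolate such a fall. For the same reason, a headcount of high-dose patients would not measure dilution, and the documents give no such headcount.

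**A reader might infer that turnover or coding biases the comparison.** This is possible but not demonstrated. With 1451 patients and 286 clinicians (section 3), about 5 each, losing one patient would cut a clinician's total by about 20% if doses were equal. With the 17 per clinician assumed in 7.1, it would be about 6%. Either figure describes one clinician. Randomization makes ordinary turnover noise unless it differs by arm, and the model allows each arm its own slope before the intervention. Booking a long supply in the month it is written is likewise hypothetical, since the example shows only 15- and 30-day supplies. PainTracker might alter which visits carry a pain code, but all pain codes count and nothing shows that visits would lose them.

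**A clinician total is a legitimate measure.** It is stated consistently in the précis, section 3 and 7.3.2, and it matches the unit of randomization in 4.2.2. That is a good reason to keep it as a measure of prescribing volume. It does not make it a measure of dose in high-dose persons.

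**Total and mean may be the same variable.** Section 7.4 can be read as the arm mean of clinician values, so a definite contradiction is not shown. The wording still permits two different constructions.

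**Conclusion.** The point holds in two parts.

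The example in 7.3.2 is internally inconsistent: 325 from the rule, narrative and first line, against 425 from the second, a difference of 100 mg or 31%. The figure 325 has the support of the narrative and the first line. The authors must confirm it, because the text alone does not settle which entry was intended. This is an illustrative calculation; no treatment dose and no sample-size figure depends on it.

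The larger part is the mismatch. Following the plan as written, the analysis would estimate a change in the volume clinicians prescribe across all qualifying visits, and would not isolate a dose change in high-dose persons. This rests on the definitions in 7.3.2 and 7.4 and needs no assumption about how many patients are high-dose. The documents do not allow the resulting loss of sensitivity to be sized.

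The benzodiazepine unit is a clerical slip whose intent is evident. Someone might read it as a flaw in the outcome, but nothing in the analysis turns on it. The primary referral outcome is not touched by any of this.

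**What to change.** 1. Reconcile the two lines of the example in 7.3.2 with the narrative. If the narrative stands, the second line and total become 200 + 100 + 25 = 325.
2. Use one definition of the MME outcome in 7.3.2 and 7.4. State the unit (clinician or patient), the denominator, and the month or months to which a prescription is assigned.
3. Test the secondary hypothesis with mean daily MME per patient per month, in patients of the cohort fixed at randomization who are classed as high-dose from baseline prescribing only. The investigators should fix the analysis cut-off in the SAP before outcome data are examined. The model should account for clustering by clinician, the unit randomized; equation [1] now has only a clinic effect.
4. Keep the clinician aggregate as a supporting measure of prescribing volume.
5. Correct the wording of the benzodiazepine unit.

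The cost is protocol and SAP wording, some programming on EHR data already being collected, and a smaller analysis set for this hypothesis. Section 7.1 bases power on the referral outcome only, so no stated power figure changes. The precision available in the high-dose group should be reported once its size is known from baseline data.
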